### **1.0 INTRODUCTION**

#### **1.1 Overview**

##### **Ductal Carcinoma in Situ (DCIS): A disease of screening with potential risks and burdens**

DCIS was rarely diagnosed prior to widespread use of mammography. Although mammography has been shown to reduce overall breast cancer mortality by over 20%, there is growing concern that for some patients, particularly those with DCIS, breast cancer screening may unintentionally cause harm by introducing additional procedures, promoting anxiety, and detecting cancers that may never cause illness. Advances in epidemiology and cancer biology have shown that the group of diseases currently deemed “cancers” are actually many conditions with enormous variation in biologic behavior, and that screening uncovers some conditions that may never impact a person’s overall health if left undetected. The term “**overdiagnosis**” has been used to define these conditions including DCIS, that look like early cancer, but are not destined to cause symptoms or death during a patient’s lifetime. Attempts to resolve the controversy that has grown around the best management of these overdiagnosed conditions, including calls to remove the word “cancer” from their description, have garnered intense interest, anxiety, and scrutiny from patients, their families, and other healthcare stakeholders.

There is a general consensus that much of this burden derives from the treatment of DCIS. Currently, almost all DCIS is treated aggressively according to guideline-concordant care (GCC); of those treated, the majority may not benefit if they would not have developed cancer. An alternative to GCC is active surveillance (AS). Currently, only 3% of women in the United States with DCIS opt for AS (if given the choice). However, in order to consider AS as a future treatment option for DCIS, it is imperative that long-term health and quality of life (QOL) outcomes resulting from AS are critically evaluated.

#### **1.2 Background and rationale**

Annually, approximately 65 million women undergo mammographic screening in the United States at a cost of over 13 billion dollars. Almost one in 1300 mammograms (.08%) will detect ductal carcinoma *in situ*, or DCIS, traditionally considered the earliest detectable form of breast cancer. Over 62,000 women in the United States will be diagnosed with noninvasive breast cancer this year alone (87% of which is DCIS, totaling over 53,000 cases per year). Almost all of these diagnoses are made in completely asymptomatic individuals. DCIS is characterized by a proliferation of malignant cells confined to the milk ducts of the breast. Unlike invasive cancer, DCIS cells remain trapped within the breast duct and therefore have little potential to spread to distant organ sites and cause symptoms or death. Without treatment, it is estimated that only 20-30% of DCIS will progress to invasive cancer. However, once diagnosed, over 97% of women are treated according to current guidelines with a combination of surgery, radiation and hormonal therapy treatments similar to those recommended to patients with invasive breast cancer. This is different than treatments for other breast conditions, such as atypical ductal hyperplasia (ADH) or lobular carcinoma in situ (LCIS), which are also known to confer an increased risk of breast cancer.

### ***Impact of DCIS on the health of individuals and populations.***

Overdiagnosis and overtreatment resulting from mammographic screening have been reported to be as high as 1 in 4 patients (25%) diagnosed with breast cancer, although the absence of standard definitions for measuring overdiagnosis has led to much uncertainty around this estimate. The national health care expenditure resulting from false positive mammograms and breast cancer overdiagnosis has been estimated to approach \$4 billion annually. There is general consensus that much of this burden derives from the treatment of DCIS; for those estimated 40,000 women per year whose DCIS may never have progressed even without treatment, medical intervention can only harm. In those women who undergo surgical management of DCIS, there is risk of developing a number of short and long-term adverse events and side effects ranging from complications of anesthesia and loss of work due to treatment, to cosmetic changes and persistent pain at the surgical site. Importantly, pain after lumpectomy may be as prevalent as that after total mastectomy with estimates ranging from 25-60%. Persistent postsurgical pain is rated by patients as the most troubling symptom, leading to disability and psychological distress, and is often resistant to management; notably, much of these data have been collected in women with cancer, not DCIS.

### ***Atypical ductal hyperplasia (ADH) is a model of active surveillance for breast conditions.***

Since over 97% of women receive treatment for their disease immediately upon diagnosis, it has been difficult to evaluate the outcomes of an AS strategy for DCIS. However, there are other analogous clinical scenarios in which women are identified to be at increased risk for breast cancer, and are routinely offered close surveillance. One such example is atypical ductal hyperplasia (ADH) which, much like DCIS, is often diagnosed on a biopsy performed for a mammographic abnormality. ADH is found in approximately 10% of all benign breast biopsies, and is associated with the highest future risk of breast cancer among all benign diagnoses. It shares many histologic features with low grade DCIS for which it is often mistaken, even by specialized breast pathologists. The lifetime cumulative risk of invasive cancer among women with ADH has been reported to approach 15% at 25 years (Figure 1a), equivalent to approximately half the risk for invasive cancer in women not recognized to have DCIS and who were thus managed with biopsy alone (Figure 1b). The treatment recommendation for women with ADH is not surgery or radiation but rather close or active surveillance, usually with the option of endocrine therapy such as tamoxifen to reduce risk of subsequent invasive cancer.

***Lobular neoplasia (LN) is another example of a risk marker for invasive breast cancer.***

Lobular neoplasia is characterized by the proliferation of uniform rounded cells which arise from the terminal ductal lobular units. These cells have relatively little cytoplasm, are dis-cohesive, and may spread along the ducts in a Pagetoid fashion. If the cells occupy and distend more than 50% of the acini, the condition is termed lobular carcinoma in situ (LCIS), otherwise it is termed atypical lobular hyperplasia (ALH). Although the distinction between the two conditions is one of degree, the more extensive changes seen in LCIS are associated with a higher risk of subsequent malignancy than occurs in ALH. Previous studies have suggested that LN is predominantly a condition found in pre-menopausal women. A study of women registered on the Surveillance, Epidemiology and End Results (SEER) database in the US shows a 38% increase in the incidence of what in the SEER database is termed LCIS between 2000 and 2009, from 2.0/100,000 to 2.75/100,000 in females aged 18-80. Two previous studies of the SEER database suggest that there has been a three to four-fold increase in LCIS diagnoses since 1978 (women with ALH were not included in these studies), predominantly among post-menopausal women. This increase is explained, at least in part, by the increasing use of screening mammography and the increasing proportion of women who undergo percutaneous needle biopsy in the investigation of screen-detected abnormalities, particularly microcalcifications.

A recent study of 1060 women with LCIS reported bilateral synchronous LCIS in only 2% of cases, and in the same series none of the 56 women who underwent bilateral prophylactic mastectomy were reported as having bilateral LN, although six had contralateral occult cancers (three invasive carcinomas and three DCIS). Lobular neoplasia has long been regarded as a marker for an increased risk of subsequent malignancy rather than as a precursor. The known increase in breast cancer risk in both breasts has been cited as a justification for this view. However, more recently, the hypothesis has emerged that, at least in some women, LN may be a non-obligate precursor of invasive malignancy. The risk of malignancy appears to be higher in LCIS than ALH, estimated to be 8-10 times and 4-5 times background incidence respectively.

There is evidence for tamoxifen to reduce the risk of invasive cancer in women with LCIS by 56% in the NSABP P-1 study published in 1998 and raloxifene to have a similar protective effect. Chemoprevention has also been shown to reduce the risk of invasive cancer in a recently published longitudinal study.

Thus, we propose that the recommended management of women with ADH and LCIS or ALH is a model for what an active surveillance (AS) approach would be for DCIS including close follow-up and the option of chemoprevention.

***Current gaps in evidence.***

In 2009, the National Cancer Institute (NCI) convened a State-of-the-Science conference that identified the most critical research questions around DCIS, including investigations on the impact of DCIS on QOL and trials evaluating the comparative effectiveness of DCIS treatment strategies. Further, the American Cancer Society and National Institutes of Health (NIH) published the summary of an NCI DCIS Workshop in 2010 that reviewed current issues in DCIS and identified risk communication as a priority area for future study. However to date, data remain lacking in all of these areas.

Current treatment options routinely offered for DCIS include surgery (lumpectomy or mastectomy),

radiation (radiation or none) and hormonal therapy (Table 1). Increasingly, some women choose to undergo bilateral mastectomy. These options constitute GCC according to National Comprehensive Cancer Network (NCCN) treatment recommendations. Between 1991 and 2010, 23.8% of women diagnosed with DCIS in the United States underwent mastectomy, 43% lumpectomy with radiation, and 26.5% lumpectomy without radiation, based on data from the Surveillance, Epidemiology, and End Points Registry. Among the 97% of women with DCIS treated with GCC, neither randomized trials or retrospective studies to date have shown a survival advantage of any treatment option over another. To date, none of the treatment options has ever been compared to AS.

**Table 1. Guideline concordant care (GCC) and Active surveillance (AS) options for DCIS.** All treatments offered as part of published guidelines mandate surgical excision to negative margins and consideration for adjuvant radiation or endocrine therapy.

	Intent	Surgery	Radiation	Endocrine Therapy
Guideline- Concordant Care (GCC)	Treatment at time of diagnosis for all patients	lumpectomy	yes	yes
			no	no
		mastectomy	no	yes
				no
Active Surveillance (AS)	Treatment only for those who progress during surveillance	none	no	no
				yes

Moreover, the impact of GCC and AS for DCIS on quality of life have not been carefully evaluated. Although research suggests that over 40% of women who are provided risk/benefit information regarding DCIS treatment would consider non-surgical management, the clinical outcomes and patient reported outcomes (PRO) of active surveillance have never been studied. Thus women (and their doctors) face a tremendous burden of uncertainty when considering the tradeoffs of GCC or AS for DCIS. This is likely compounded by the relative lack of information and heterogeneity in opinions regarding the optimal treatment of DCIS.

***Potential for study to improve health care and outcomes.***

This year in the United States alone, approximately 50,000 women will undergo treatment for DCIS, of whom only 20-30% may benefit. Evidence to compare clinical outcomes and patient reported outcomes between GCC and AS is critically needed to reduce the harms and understand the trade-offs of GCC versus AS for DCIS. This project will provide clear, objective, evidence-based information for patients, health care providers and other stakeholders regarding the benefits and harms of DCIS treatment. Moreover, this project will create a path forward for mitigating the potential for overtreatment of other screen-detected conditions.

**2.0 OBJECTIVES**

**2.1 Relationship of aims to significance of the proposed study.**

The overarching goal for this study is to evaluate the benefits and harms of currently accepted GCC for DCIS compared to an active surveillance (AS) strategy using cross-sectional patient survey data. The broad, long-term objective of this project is to enable patients with DCIS, with their doctors, to make

informed decisions about their care based on the highest possible quality evidence about DCIS treatment, including those treatment options that fall outside of current GCC.

## **2.2 Hypothesis and Specific Aims:**

We hypothesize that there are differences in patient-centered clinical outcomes and Patient Reported Outcomes (PROs) between women who choose GCC versus AS, and that these differences can be compared using advanced analytic methods to allow for the expected treatment selection biases between groups.

The specific aims of this study are the following:

**Aim 1. Compare patient-reported outcomes (PROs) between patients diagnosed with ductal carcinoma in situ (DCIS) who received GCC to patients diagnosed with DCIS who underwent AS as well as those diagnosed with atypical ductal hyperplasia (ADH), and lobular carcinoma in situ LCIS/atypical lobular hyperplasia (ALH) (as proxies for DCIS active surveillance (AS) group) in a cross-sectional patient cohort at 6 selected study sites.**

PROs will be collected from surveys administered to patients diagnosed for either DCIS, ADH, LCIS, or ALH between January 1, 2012 and June 30, 2017 at each of six study sites: Duke University Medical Center (DUMC), Dana-Farber Cancer Institute (DFCI), MD Anderson Cancer Center (MDACC), Massachusetts General Hospital (MGH), Newton Wellesley Hospital (NWH), and Dana-Farber/Brigham and Women's Cancer Center (DF/BWCC) in clinical affiliation with South Shore Hospital (DFCI @ SSH). We are planning for survey data collection to begin in September 2017, but will officially commence upon IRB approval at each recruiting site. MDACC received their site's IRB approval on December 6, 2017 and has now been added to the DFCI IRB as a site. MDACC will now complete applicable study procedures as outlined in this protocol. DUMC received their site's IRB approval on February 27, 2018 and has now been added to the DFCI IRB as a site. Duke will now complete study procedures as outlined in this protocol. MGH has been added to the DFCI IRB as a site. MGH will now complete study procedures as outlined in this protocol. DFCI @ SSH has been added to the DFCI IRB as a site. DFCI @ SSH will now complete study procedures as outlined in this protocol. The DFCI study team will complete all patient recruitment steps for DFCI @ SSH. NWH has been added to the DFCI IRB as a site. NWH will now complete study procedures as outlined in this protocol.

Once enrollment begins at a site, the recruitment and survey phases will take place over an 18-month period, or until we reach our enrollment goal. Medical records will be accessed through the duration of the recruitment phase, which we anticipate will be completed in 2019, to look for potentially eligible patients for this study. The primary study outcome will be postoperative pain, assessed on a 10-point Likert Scale as well as on the pain burden index. In addition, other PRO instruments will be administered to evaluate QOL measures including symptom assessment, decision quality, body image, and anxiety to better understand the overall benefits and harms of a GCC approach versus an AS approach.

**Aim 2. Measure the incremental utility of GCC compared to AS according to a preference-based quality-adjusted life year metric (QALY).**

We have developed an 8-item questionnaire based on a time trade off model to collect a preference-based measure of health on the cohort in Aim 1. This tool will be included in the patient survey and data collected from this tool will be used to compare a standardized health utility measure of GCC versus AS. This deliverable will allow patients and stakeholders to better weigh the benefits and tradeoffs of each approach.

### **3.0 RESEARCH SUBJECT SELECTION:**

This study will be conducted at 6 NCI Comprehensive Cancer Center sites (DUMC, DFCI, MDACC, MGH, NWH, and DFCI @ SSH). Additional study sites may be considered to enhance accrual.

The GCC group will be those patients diagnosed with DCIS and treated according to one of the standard treatment options for DCIS (Table 1). Importantly, since only 2-3% of all women diagnosed with DCIS are offered and/or undergo active surveillance, there are insufficient numbers of women with DCIS solely electing AS to compare with women treated according to GCC, even across 3 large volume cancer centers. Therefore, we decided to add to our DCIS AS group, those patients who have a similarly high breast cancer risk based on a diagnosis of ADH, ALH, or LCIS for whom the routine recommendation is active surveillance. The ADH/ALH/LCIS group will thus serve as an additional proxy for the DCIS active surveillance group, since these risk lesions are managed with a follow up and surveillance approach as could be applied if AS were to be used for low risk DCIS. This design will allow the most relevant comparison of PROs between GCC and AS strategies for conditions associated with increased breast cancer risk.

English and Spanish speaking patients diagnosed for either: DCIS, ADH, ALH and/or LCIS between 2012 and 2016 will be included. Each site has a large patient volume of DCIS cases treated and specific expertise in studying a DCIS patient population. Moreover, the sites have unique and complementary patient populations, with a large African American population treated at DUMC (26.7% of all patients with DCIS treated 2011-2013) and a sizable Hispanic population treated at MDACC (12.8% of all patients with DCIS treated 2011-2013).

***Eligibility Criteria.*** Patients treated at DUMC, DFCI, MDACC, MGH, NWH, or DFCI @ SSH with a diagnosis of DCIS, LCIS, ADH, or ALH who are also:

- Age 18 or more at index diagnosis
- Diagnosed with DCIS, LCIS, ADH, or ALH (the most recent, highest risk lesion is the “index lesion”) between January 1, 2012 and June 30, 2017
- Able to read either English or Spanish and able to provide written (via paper), verbal consent or on-line informed consent
- Treated and followed at one of the study sites (including affiliated network sites) and for whom treatment and surveillance data are available, for at least 1 year of follow up after date of diagnosis
- Participants with bilateral synchronous or metachronous disease (DCIS, LCIS, ADH, ALH) are eligible

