#### **4.0 RESEARCH SUBJECT ENTRY**

All activities will be conducted through the 6 study recruitment sites, who will handle all eligibility for their own site's patients. The DFCI main study site will screen and recruit for its own patients as well as for DFCI @ SSH patients. Patients will be recruited individually to the trial. All women with DCIS, LCIS, ADH or ALH newly diagnosed between January 1, 2012 and June 30, 2017 and treated at one of the 6 designated study sites will be identified systematically at each study site using cancer registry and clinic, radiology, and pathology record review. We will collect consecutive cases in a retrograde fashion starting from June 30, 2017 to January 1, 2012 until we have collected 900 DCIS cases and 300 LCIS, ADH, or ALH cases.

In order to assess eligibility and initiate entry into the study chart review necessary for Aim 1 of the study, we will request approval of a waiver of informed consent and a waiver of HIPPA. Once approved, a research coordinator at each site will review clinic, radiology, pathology, and tumor registry lists to screen for potential candidates, and identify potentially eligible patients. We will extract the following from the medical record for potential participants:

- Name
- Contact information (i.e. mail address, phone number and/or email address)
- Age
- Race/Ethnicity
- Date and type of last biopsy
- Date and type of last surgery
- How lesion identified and relevant mammography
- Pathologic features of the disease on core biopsy (if DCIS: grade, necrosis, ER, PR/HER2 if done, size, microinvasion)
- Type of subsequent evaluation of lesion (excision, surgery etc.) and any subsequent breast pathology or procedure
- Any adjuvant treatment
- Date and vital status at last follow-up; we will plan to complement this with a National Death Index (NDI)/Institutional database look to make sure potential participants are available before contacting them.

Sites responsible for screening patients and their affiliates will use the eligibility information above for their patients to determine eligibility. We will also use these data to describe the patient population and the disease characteristics of these non-invasive breast lesions at diagnosis.

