### **5.5 Description of the study process**

#### **5.5.1 Survey Administration**

We will recruit approximately 900 women with DCIS matched 3:1 to women with ADH or LCIS/ALH (proxies for AS group) or DCIS choosing AS identified at 6 geographically and demographically distinct study sites: DUMC, DFCI, MDACC, MGH, NWH, and DFCI @ SSH. Any patients who have selected AS for DCIS will specifically be identified and contacted for inclusion in the study. Enrolled patients will be asked to complete a one-time survey. The recruitment and survey phases will take place over an 18-month period once enrollment begins. We anticipate data cleaning and analysis will last 6 months.

The study coordinator at each site or the lead for an affiliate site will verify the mailing address and/or email address for each eligible patient, then local study staff will send an invitation letter and response form (Appendix A). The invitation letter and response form will include information about the study, study coordinator contact information, and will ask participants to send the local site their email address in order to receive the link to the study materials including an online elements of consent information page and online survey (Appendix B), or their address to receive the consent and survey (Appendix B) via mail. The contact information of all women who agree to participate in the study will be sent from the local study team to the DFCI study team to contact potential participants to initiate the consenting and survey process (Appendix B). In DFCI's initial application, it was requested and approved, to have a waiver of documentation of consent for people who complete the survey online or on the phone.

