### **6.2 Sample size and statistical power**

Importantly, published data indicate that patients undergoing lumpectomy with radiation report comparable levels of pain and sensory disturbances as those undergoing mastectomy. Thus, these treatment groups will be grouped together in the initial analysis, then a stratified analysis will be performed. Preliminary data among 582 women undergoing either lumpectomy or mastectomy indicate that the mean persistent pain intensity after breast surgery is 2.61 (DS 4.24). Given a sample size of 900 patients in the GCC group and 300 in the AS group, we will be able to detect with 90% power at a level of 0.05 (2-sided) a difference in pain intensity score of 2 (from 2.61 to 0.61), which has been deemed to be a clinically meaningful difference.

Based upon the number of unique cases diagnosed with DCIS at each site between 2010 and 2013, we estimate that at all 6 study sites combined, approximately 1500 women will have been diagnosed with DCIS between January 1, 2012 and June 30, 2017 and will be eligible to participate. Our response rate in prior survey studies has been approximately 60% using the approach we will adapt to the current study; thus, we anticipate that about 900 women with DCIS will be accrued and will complete the survey across all study sites. These patients will be matched 3:1 to participants diagnosed with ADH or LCIS/ALH undergoing active surveillance. DCIS participants will be matched 3:1 to ADH/LCIS/ALH participants, based on matching criteria of age within 5 years, year of diagnosis, and study site. Additional matching criteria such as race, income, highest education level attained, and family history of breast cancer will be considered based upon stakeholder input during the protocol preparation process.

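### ADH/ALH/LCIS proxies join the AS group by diagnosis, with no rule on surgery received; this conflicts with Table 1 and can dilute the pain contrast by an unknown amount

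*Protocol*

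**What the plan says.** Table 1 (Protocol 1.2, on gaps in evidence) gives the AS row as surgery none and radiation no, with the intent "Treatment only for those who progress during surveillance".

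Protocol 3.0 defines the two sides differently. GCC requires a DCIS diagnosis and treatment by a standard option. The proxies need only a diagnosis of ADH, ALH or LCIS, lesions "for whom the routine recommendation is active surveillance". The section concludes: "The ADH/ALH/LCIS group will thus serve as an additional proxy for the DCIS active surveillance group".

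No inclusion or exclusion criterion in 3.0 mentions surgery. Section 4.0 collects consecutive cases by lesion until there are 900 with DCIS and 300 with LCIS, ADH or ALH.

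Surgery is recorded. Section 4.0 abstracts "Type of subsequent evaluation of lesion (excision, surgery etc" and the date and type of the last surgery; 5.4 adds prior breast surgery. Section 6.3 (Protocol and SAP) names endocrine treatment, radiation and comorbidity as examples of factors to control, but not surgery.

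Two texts point the other way. Section 6.2 (Protocol and SAP) describes the matched proxies as being under active surveillance. Section 5.5.1 brings DCIS women into the AS side by management: "or DCIS choosing AS identified at 6 geographically and demographically distinct study sites".

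**The concern.** The primary endpoint is pain, and the planned contrast (2.61 against 0.61) takes its higher mean from women who had lumpectomy or mastectomy. The AS side is meant to show pain without that surgery. Under the selection rules as written, a woman with ADH or LCIS who had an excision or a mastectomy meets every criterion and counts towards the 300.

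The protocol itself shows that such surgery occurs. Its background on lobular neoplasia cites a series of 1060 women with LCIS and refers to "none of the 56 women who underwent bilateral prophylactic mastectomy". It also says, in 1.2, that pain after lumpectomy may be as common as after mastectomy, so on its own premise limited surgery matters.

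Operated women on the AS side raise that group's mean pain and shrink the difference. Without a written rule, their classification could also be settled after the data have been seen.

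**Working it through.** **Inputs (section 6.2).** "Given a sample size of 900 patients in the GCC group and 300 in the AS group"; mean 2.61, SD 4.24, difference 2, two-sided 0.05, stated power 90%.

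**The plan's own figure.** Normal approximation, common SD, matching ignored:

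- SE = 4.24 × √(1/300 + 1/900) = 0.283.
- 2 / 0.283 = 7.08, so power exceeds 99.99%. The stated 90% is not reproduced; it is conservative, and this point does not depend on it.
- Difference detectable with 90% power: (1.960 + 1.282) × 0.283 = 0.92.

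**Dilution model (assumption).** Let p be the share of the AS group with breast surgery, and f the fraction of the GCC pain excess that this surgery causes. If all 300 are proxies, as section 4.0 counts them, p is the operated share of proxies.

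- AS mean = 0.61 + 2fp
- Observed difference = 2(1 − fp)

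The documents give neither p nor f. The only related figure is 56/1060 = 5.3%, for bilateral prophylactic mastectomy in the cited LCIS series. The other values of p show the range.

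| p | Difference, f = 1 | Power, f = 1 (900 vs 300) | Difference, f = 0.5 |
|---|---|---|---|
| 5.3% | 1.89 | >99.9% | 1.95 |
| 25% | 1.50 | >99.9% | 1.75 |
| 30% | 1.40 | 99.9% | 1.70 |
| 50% | 1.00 | 94% | 1.50 |
| 60% | 0.80 | 81% | 1.40 |
| 80% | 0.40 | 29% | 1.20 |

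With f = 1, power falls to 90% when 2(1 − p) = 0.92, at p of about 54%. Allowing for the extra variance of a mixed AS group changes little (93% rather than 94% at p = 50%).

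**Can the study afford to set operated proxies aside?** With 60 AS women against 900 GCC, SE = 4.24 × √(1/60 + 1/900) = 0.565, 2 / 0.565 = 3.54, and power for 2 points is 94%. With 30 it is 72%.

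**Counting of DCIS women on AS.** Section 6.2 reaches 900 as 60% of about 1500 women with DCIS, then treats 900 as the GCC group. Section 3.0 puts AS at 2–3% of women with DCIS: 0.02 × 900 = 18 to 0.03 × 900 = 27. If all of them stayed in GCC with AS-like pain, the GCC mean would fall by 2 × 0.02 = 0.04 to 2 × 0.03 = 0.06 points.

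**The case against.** - A reader might infer that the whole AS group is formed by diagnosis. It is not: Aim 1 and 5.5.1 bring in DCIS women by the management they had. Only the proxy part is affected.
- A reader might infer that the plan deliberately counts operated proxies as surveillance. Nothing says so. Section 6.2 describes the proxies as under surveillance, and 3.0 says these lesions are managed by follow-up. What stands is that neither statement is made a rule.
- The chart field for excision or surgery is one list for all candidates, DCIS included, so it does not show that surgery is expected among proxies. The 56 mastectomies come from one LCIS series and say nothing about ADH or ALH.
- Assuming f = 1 is severe. The comparability of pain in 6.2 concerns lumpectomy with radiation against mastectomy, not a diagnostic excision alone. This stands, and f is left open for that reason.
- Control for other treatment in 6.3 is an open list and might be stretched to surgery. But surgery largely defines GCC, so adjusting for it would not repair a misassigned group.
- Removing every operated proxy carries its own bias. Table 1 allows treatment on progression, so removal would condition on later events and could keep the women who did well. This objection stands and shapes the fix.

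**Conclusion.** The point holds for the proxy women. Sections 3.0 and 4.0 select them by diagnosis and routine recommendation, with no criterion on surgery received; this conflicts with Table 1 and with the description in 6.2.

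The size is unknown. The one figure in the documents moves 2.0 only to 1.89, even at f = 1. Larger losses need operated shares that the documents do not give. At low or moderate shares the cost is a biased estimate, not lost power.

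A reader might conclude that the study will understate the harm of GCC. The documents do not support that as a statement about the net result. The pull towards zero belongs to this mechanism, on the protocol's premise that surgery raises pain. The groups also differ by diagnosis, and other confounding could move the contrast either way.

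A reader might also conclude that DCIS women on AS will be analysed as GCC. Sections 3.0 and 5.5.1 place them on the AS side. The 900 in 4.0 is an accrual count, and 6.2 equates it loosely with GCC. That is a wording inconsistency worth at most 0.04–0.06 points.

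This should be fixed before analysis; confidence is moderate.

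**What to change.** 1. Reconcile 3.0 and 4.0 with Table 1 and 6.2, so that one written rule decides which proxies belong to AS.
2. Derive surgery status for proxies from the fields in 4.0 and 5.4. Separate surgery as initial management of the index lesion, with diagnostic excision flagged, from surgery after a period of surveillance.
3. For the primary comparison, define AS as women without therapeutic or prophylactic surgery or radiation as initial management of the index lesion. Women operated on after a period of surveillance then stay in AS, consistent with the intent in Table 1.
4. Report the proportion of proxies operated on, by type and timing.
5. Run the pain comparison with and without operated proxies, including a run that leaves out diagnostic excisions.
6. State in 4.0 and 6.2 that DCIS women on AS count in the AS group and not among the 900 GCC.

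Cost: wording, a derived variable and a few extra analyses. The AS group becomes smaller, although 60 women would still give 94% power for 2 points. Section 4.0 dates only the last biopsy and last surgery, so women with several procedures may need a further chart check to establish timing.
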